6.1 INTERIM ANALYSIS

This trial will employ an adaptive design for the blinded re-estimation of the sample size. To ensure the study is adequately powered for the superiority comparison for the primary outcome measure, the assumptions regarding the rates of AF in both study arms will be verified after 50% of the originally planned total patient sample have complete primary endpoint information. A conditional power (CP) approach for sample-size re-estimation using the Mehta-Pocock approach will be utilized. Following this interim assessment, the sample size may only remain the same or be increased. A third-party, independent statistician will perform this analysis to minimize operational bias. This analysis will occur after approximately 50% of the originally planned subjects a completed/analyzable primary endpoint. The statistician will assess the conditional study power assuming that the hazard ratio remains the value estimated at this analysis. The conditional power will be categorized into one of the three following zones:

Favorable: CP ≥ 80%

Promising: 36% ≤ CP < 80% Unfavorable: CP < 36%

The lower bound on the promising results is selected from Mehta and Pocock as a function of the target power, timing of the sample size re-estimation, and maximum sample size. Selection of this boundary in particular does not inflate the overall Type I error rate. After the analysis, the statistician will provide a recommendation to the Steering Committee and Volta Medical clinical team:

- In the event that the conditional power is found to be in the Unfavorable zone, the study will continue to the originally planned sample. The independent statistician will report ONLY that the trial will continue as originally planned.
- In the event that the conditional power assessment is Promising, the sample size will be increased to 100 total subjects (an additional 50 maximum per treatment arm, predetermined by Volta). The independent statistician will report that the sample size should be increased and by how many subjects (in regard to the 292 subjects originally planned).
- In the event that the conditional power is found to be in the Favorable zone, the study will continue to the originally planned sample. The independent statistician will report ONLY that the trial will continue as originally planned.

Also, the following information will be shared with senior, non-operational management staff that have a strict business need to review and act on the results:

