- The recommendation (sample size increase or continue as originally planned)
- The rate of freedom from AF for each arm for the overall interim analysis population
- The rate of freedom from AF for each arm for two subgroups depending on the AF type (persistent AF and long-standing persistent AF)

None of the clinical operational staff or study investigators will have access to the interim data on which the analysis is based to further minimize operational bias. The scientific soundness of the study is not likely to be impacted as the only potential change to the study as a result of this analysis is an increase in sample size.

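### The sample-size re-estimation is labelled blinded but is unblinded, and SAP 6.1 gives senior management by-arm AF-free rates that the keep-or-increase decision does not need

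*SAP*

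**What the plan says.** SAP 6.1 opens with "This trial will employ an adaptive design for the blinded re-estimation of the sample size", and protocol 6.6 uses the same sentence. Both name a Mehta-Pocock conditional power method, applied "after 50% of the originally planned total patient sample have complete primary endpoint information". SAP 6.1 then specifies the calculation: "The statistician will assess the conditional study power assuming that the hazard ratio remains the value estimated at this analysis". The zones are favorable (conditional power of 80% or more), promising (36% to below 80%) and unfavorable (below 36%).

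On reporting, "the statistician will provide a recommendation to the Steering Committee and Volta Medical clinical team". In the favorable and unfavorable zones the message is the same: only that the trial continues as planned. In the promising zone, "the sample size will be increased to 100 total subjects (an additional 50 maximum per treatment arm, predetermined by Volta"), and the statistician reports the increase relative to the 292 planned.

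Senior, non-operational management receives the recommendation and two further items:
- "The rate of freedom from AF for each arm for the overall interim analysis population"
- those by-arm figures split by AF type, once for persistent and once for long-standing persistent AF

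SAP 6.1 adds: "None of the clinical operational staff or study investigators will have access to the interim data". For the management group, protocol 6.6 names only the recommendation. It leaves the procedures for conducting, reporting and acting on the analysis to the SAP.

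**The concern.** A re-estimation described as blinded is normally understood to use pooled data only and to reveal nothing about the treatment effect. Someone approving this plan on that understanding would not look for rules on who may see arm-level results. Here the calculation depends on the estimated effect, so those rules matter.

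The SAP does have one: the two outer zones are reported identically, so recipients cannot tell a trial going well from one going badly. The by-arm rates undo this for the management recipients, who can read the effect directly and work back to the zone. They can act only on whether to keep or raise the sample size, and the recommendation already settles that. The rates by AF type do not enter the rule at all.

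The promising-zone sentence is an operative instruction and, read literally, would set the trial's size at 100.

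**Working it through.** **Inputs.** AF-free 62% and 77%, HR 0.547, 292 evaluable, 374 enrolled, 22% drop-out, one-sided alpha 0.025, 80% power (SAP 4.2.2; protocol 6.2 and 6.3). Zone limits 36% and 80% (SAP 6.1). Assumed here: information fraction t = 0.5, proportional hazards, control arm at exactly 62%.

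**The plan's own figures reproduce.** ln(0.77)/ln(0.62) = 0.547. A numerical log-rank calculation (exponential survival, 12 months' follow-up) gives power 0.800 at N = 292. Drop-out: 292/0.78 = 374.4.

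**Zone limits on the z scale.** CP = Φ[(z₁/√t − 1.96)/√(1−t)], so z₁ = √t·[1.96 + √(1−t)·Φ⁻¹(CP)].
- CP 36%: z₁ = 1.207
- CP 80%: z₁ = 1.807

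**Events at the interim.** Half of the planned sample can mean 146 of 292 or 187 of 374.
- 146 patients: 73 × (0.38 + 0.23) = 44.5 events
- 187 patients: 93.5 × 0.61 = 57.0 events

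**Limits as hazard ratios and Tailored rates.** HR = exp(−2z₁/√events); Tailored rate = 0.62^HR. Events are held at the design number, which is an approximation.

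| Interim | Unfavorable if HR above | Tailored rate below | Favorable if HR below | Tailored rate above |
|---|---|---|---|---|
| 146 patients | 0.697 | 71.7% | 0.582 | 75.7% |
| 187 patients | 0.726 | 70.7% | 0.620 | 74.4% |

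A direct check with 73 per arm, letting events follow the rates, agrees: Tailored 77% gives CP of about 90%, 74% about 65%, 72% about 43% and 70% about 24%.

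**What the word to continue reveals alone, at HR 0.547.** Take z₁ ~ N(−ln(0.547)·√events/2, 1).
- 44.5 events: mean 2.013. Favorable 0.582, promising 0.208, unfavorable 0.210. P(unfavorable given continue) = 0.210/(0.210 + 0.582) = 0.265, about 27%.
- 57.0 events: mean 2.278. Favorable 0.681, promising 0.177, unfavorable 0.142. P(unfavorable given continue) = 0.142/(0.142 + 0.681) = 0.172, about 17%.

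The two overall rates largely remove that uncertainty.

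**Precision by AF type.** If long-standing AF sits at its 15% floor (protocol 5.2.1), there are 0.15 × 146/2 ≈ 11 or 0.15 × 187/2 ≈ 14 such patients per arm. The 95% half-width at 62% is 1.96·√(0.62 × 0.38/n), or 29 or 25 points. This is the worst case; a larger share narrows it.

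**The increase.** Fifty more per arm is +100.
- Added to 292 evaluable: 392, and 392/0.78 ≈ 503 enrolled.
- Added to 374 enrolled: 474, and 474 × 0.78 ≈ 370 evaluable.

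**Type I error.** With the final critical value left at 1.96 and total information r relative to plan, the conditional rejection probability under the null is 1 − Φ[(1.96√r − z₁√t)/√(r−t)]. Here r = 1 outside the promising zone and at most 392/292 inside it. Integrated over z₁ ~ N(0,1):
- fixed +100: 0.0244
- increase sized to reach 80% CP, capped at +100: 0.0246
- least favorable choice within the cap: 0.0250

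**The case against.** The case for leaving the text alone has substance. Protocol 6.6 hands reporting to the SAP and describes the management recipients as needing to review and act on the results; SAP section 3 says the SAP prevails. The recipients are non-operational, operational staff and investigators have no access, patients and the ECG core lab are blinded (SAP 6.6), and the only possible change is an increase under a fixed rule.

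Most of this stands. It means that the by-arm release is wider than the protocol describes but is not a breach. Its absence from SAP section 7 is not clearly a fault either, since the protocol assigned the detail to the SAP. It also limits the risk of operational bias. It does not make the calculation blinded, and authority to release the rates does not supply a need for them. A justified release behind a documented firewall would be defensible, but SAP 6.1 gives neither a reason for the by-arm rates nor a rule keeping recipients out of later analysis decisions.

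Two stronger readings are tempting:
- **That by-arm results prompted the dropping of gatekeeping in SAP 1.4.** The documents do not support this. The released rates concern AF, whereas the gatekept efficacy endpoints concern AF/AT; section 7 gives a reason that does not depend on data; and nothing says that the rates were released or that their recipients wrote the SAP.
- **That the 36% bound inflates alpha.** At a ratio of 392/292 and half the information, the increase never raises conditional error only above a CP of about 43%. Overall type I error still comes to about 0.0244 to 0.0250.

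**Conclusion.** Three things are wrong as written. The blinded label contradicts the specified calculation, in both documents. The by-arm release defeats, for its recipients, the SAP's own rule of reporting both outer zones identically, and it serves no permitted decision. The total of 100 subjects is impossible against 292 planned, and the base for the increase is not settled: the reference to 292 favors evaluable patients, but an increase on 374 enrolled is not excluded.

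The size of the disclosure is a zone readable from the Tailored rate, with cut-offs of about 72% and 76% (146 patients) or 71% and 74% (187 patients), in place of a residual 27% or 17% chance of the unfavorable zone at the design HR. These figures rest on control at 62%, 50% information and proportional hazards; other control rates move the cut-offs but not the principle. This is a matter of labelling and information flow. It is not evidence of misuse, and the release does not alter nominal alpha.

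**What to change.** - In SAP 6.1 and protocol 6.6, replace the blinded wording with *unblinded re-estimation performed by an independent statistician*.
- Delete the two by-arm items from SAP 6.1, release only the recommendation, and keep arm-level results with the independent statistician until database lock. If by-arm rates have already been released, record the date and recipient roles in the SAP.
- State the promising-zone action as *increased by up to 100 subjects (50 per arm)*. The sponsor should say whether this is added to the 292 evaluable or the 374 enrolled, and print the matching enrolled total: about 503 if 392 are to be evaluable at 22% drop-out, 474 if added to 374.
- Leave the 36% bound unchanged.

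The cost is wording in two documents, and management loses an early look at by-arm rates. The zone rule, data collection and interim timing do not change. Printing the enrolled total settles a figure that is now open, and only the sponsor can supply it.

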6.2 BLANKING PERIODS

After the index procedure, a 3-month blanking period + tolerance of 1 week (98 days) will be applied for all efficacy endpoints, during which recurrences of AF/AT (excluding repeat procedure) will not be counted.

If a repeat procedure is performed during the 3-month blanking period (and patient is in spontaneous AF), the recurrence and the repeat procedure will be counted as occurring at 3 months.

If a repeat procedure is performed after the end of the 9th month, the procedure will not be considered for multiple procedures endpoints.

After a repeat procedure, a 2-week blanking period (14 days) will be applied, during which AF/AT recurrences will not be counted. Any re-repeat procedures (repeat procedure #2) will result in the data being censored at the time of the re-repeat procedure.

Note: for the purpose of counting months to establish blanking period boundaries in the study, one month will be considered equal to 30.4 days.

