## IV – ENDPOINTS OF THE CLINICAL INVESTIGATION

### 4.1 – Primary endpoint

The primary endpoint is defined in Table 2.

Table 2: Primary endpoint

Endpoint	Description
Long-term effectiveness primary endpoint	
1. Freedom from documented AF*, with or without AADs, 12 months after a single index ablation procedure.
 
*Freedom from documented AF is defined as no documented episodes of AF > 30 seconds with conventional non-invasive monitoring (Holters, TTM and 12-lead ECG recordings) between 3 and 12 months after index procedure
 
Difference of freedom from arrhythmia between the arms will be analyzed as comparison of survival distributions of the two arms in order to take into account the time to arrhythmia recurrence and the censored data (cf. 6.5 – Evaluation criteria for primary and secondary endpoints)

Possible scenarios that may result in primary endpoint failure:

- A repeat procedure where AF is confirmed during the procedure
- A 30-second or greater episode of AF is documented on a 24-hour Holter prior or subsequent to a follow-up visit
- 30-second of AF on a weekly TTM transmission confirmed by 30-second of AF on same or next week TTM transmission
- A 10-second 12-lead ECG recording confirming AF suggested by either TTM or Holter and subject symptoms

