### 5.3.8 – Blanking periods

After the index procedure, a 6-week absolute blanking period will be applied, during which a repeat procedure is not allowed, only cardioversions are allowed if necessary.

After this absolute blanking period and before the end of the standard 3-month blanking period, a repeat procedure is discouraged but not prohibited. The decision to perform a repeat procedure before the end of the 3-month blanking period is left to the operator's discretion. If a repeat procedure is performed during the 3-month blanking period, the recurrence and the repeat procedure are counted as occurring at 3 months.

After a repeat procedure, a 2-week blanking period will be applied, during which AF/AT recurrences will not be counted. Any re-repeat procedures will be performed outside the study according to the operator's preferred approach and will result in the data being censored at the time of the re-repeat procedure. The patient will however stay in the study for safety purposes.

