4.2 PRIMARY ENDPOINT

Freedom from documented AF, 12 months after a single index ablation procedure to be understood as a single AF ablation procedure (i.e. including redo procedures for non-AF indications).

4.2.1 **Hypotheses**

Freedom from documented AF after 12 months will be higher in the tailored group than the anatomic group.

The null and alternative hypotheses are as follows:

$$H_0: S_1(t) = S_2(t)$$

$$H_A: S_1(t) > S_2(t),$$

where S1(t) and S2(t) represent the survival functions for the Tailored and Anatomical arms, respectively, at any given time t.

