4.3 SECONDARY ENDPOINTS

The secondary endpoints are as follow:

- 1. Freedom from AF/AT after one or two procedures at 12 months following index procedure.
- 2. Freedom from AF/AT after a single procedure at 12 months following index procedure.
- 3. The safety endpoint is a composite endpoint, the events of which it is comprised include that of death, cerebrovascular event, or serious treatment-related adverse event at the 12-month timepoint since initial index procedure (this endpoint is inclusive of the Blanking Period marked by the 3 months immediately following the initial index procedure undergone by each enrolled subject).

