4.5.1 Other Adverse Events

All adverse events will be summarized through 12 months. The proportions of subjects with events will be reported. No imputation for missing data is planned.

Tabular summaries by treatment group of all adverse events, adverse device effects, serious adverse events, and serious adverse device effects will be presented.

An adverse event (AE) is defined as any untoward medical occurrence, unintended disease or injury or untoward clinical signs (including an abnormal laboratory finding) in subjects,

users or other persons, whether or not related to the investigational medical device. An Adverse Device Effect (ADE) is defined as an adverse event related to the use of an investigational medical device. A serious adverse event (SAE) is an adverse event that:

- a) led to a death
- b) led to a serious deterioration in the health of the subject, that either resulted in: a life-threatening illness or injury, or a permanent impairment of a body structure or a body function, or in-patient or prolonged hospitalization, or -medical or surgical intervention to prevent life threatening illness or injury or permanent impairment to a body structure or a body function.
- c) led to fetal distress, fetal death or a congenital abnormality or birth defect. A serious adverse device effect (SADE) is an adverse device effect that has resulted in any of the consequences characteristic of a serious adverse event.

The investigator will assess each adverse event for its relationship to the study device, and whether it was anticipated in the protocol. The determination of the relationship between the adverse event and the device is made according to the following definitions:

- Definitely related (causal relationship)
- Probably related
- Possibly related
- Not related
- Unknown.

Acute peri-procedural complications (related to the study procedure and occurring within one week of the ablation procedure), will be specifically analyzed as part of the exploratory endpoints.

5 Assessing the Primary Outcome

Freedom from documented AF between 3 and 12 months following the index ablation procedure will be defined as no documented episodes of AF > 30 seconds with conventional non-invasive monitoring.

The following scenarios result in primary endpoint failure:

- 1) A repeat procedure where AF is confirmed during the procedure (Patient is in spontaneous AF at the beginning of the procedure)

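### SAP 6.2 scores a blanking-period redo only if the patient is in spontaneous AF, so a patient re-ablated in AT can count as AF/AT-free after one procedure

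*SAP*

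**What the plan says.** **Protocol.** Section 5.3.8 bars a redo in the first 6 weeks. From then to 3 months it discourages a redo but leaves it to the operator. Its scoring rule carries no rhythm condition: "If a repeat procedure is performed during the 3-month blanking period, the recurrence and the repeat procedure are counted as occurring at 3 months". Section 4.1 lists, among the scenarios that may lead to primary failure, "A repeat procedure where AF is confirmed during the procedure".

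**SAP.** Section 6.2 sets a 98-day blanking period that "will be applied for all efficacy endpoints, during which recurrences of AF/AT (excluding repeat procedure) will not be counted". The next sentence is the only one that scores a redo within that period, and it is conditional: "If a repeat procedure is performed during the 3-month blanking period (and patient is in spontaneous AF), the recurrence and the repeat procedure" are dated at 3 months. Section 5, item 1, puts the same condition on the primary failure scenario: "Patient is in spontaneous AF at the beginning of the procedure". Section 4.2 reads the primary's single index procedure as one that is "to be understood as a single AF ablation procedure (i.e. including redo procedures for non-AF indications". Section 4.3, item 2, is "Freedom from AF/AT after a single procedure at 12 months following index procedure" and has no such reading attached.

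**Censoring and precedence.** SAP 4.2.3 censors subjects lost to follow-up. SAP 4.1.2 and 6.2 censor at a third procedure. Nothing censors at a second. SAP section 3 gives the SAP precedence over the protocol. SAP section 7 lists two changes from protocol (the primary hypothesis and the dropped gatekeeping), and this is not one of them.

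**The concern.** Protocol 4.2 counts atrial arrhythmia documented between 3 and 12 months. A redo inside blanking therefore needs a rule that carries it forward to 3 months. Protocol 5.3.8 does this for every such redo; SAP 6.2 does it only when the patient is in spontaneous AF.

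For an endpoint in which AT is itself an event, a test based on AF alone is the wrong test. It lets a patient who had an endpoint arrhythmia and a second ablation be reported as free of AF/AT after one, and that success may be due to the second ablation. The endpoint has its own superiority statement at one-sided 0.025 (SAP 4.3.1), with no multiplicity correction (SAP 6.9).

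For the primary the gap is narrower. A patient with recurrent AF may be cardioverted during blanking, which protocol 5.3.8 allows, and then be re-ablated for AF while in sinus rhythm. That patient has had two AF ablations but is neither a failure nor censored. This does not fit SAP 4.2's own "single AF ablation procedure (i.e. including redo procedures for non-AF indications", because the indication was AF.

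Only the patient is blinded to arm (protocol 5.1.1). Whether to re-ablate early is decided by an operator who knows the arm.

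**Working it through.** **1. Scoring under each rule.** Take a redo at week 10, inside both the 3-month and the 98-day limits, with no arrhythmia documented afterwards.

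| Rhythm at start of redo | Protocol 5.3.8 | SAP, single-procedure AF/AT | SAP, primary |
|---|---|---|---|
| Spontaneous AF | Event at 3 months | Event at 3 months | Event at 3 months |
| AT | Event at 3 months | No event, not censored: success | No event; intended by SAP 4.2 when the indication is non-AF |
| Sinus rhythm, redo for AF | Event at 3 months | No event, not censored: success | No event, not censored: success after two AF ablations |

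**2. The plan's sample size.** Inputs from SAP 4.2.2: 62% and 77% free from AF, one-sided alpha 0.025, power 80%, 22% drop-out.

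- HR = ln(0.77)/ln(0.62) = 0.5467, stated as 0.547.
- Lakatos log-rank method (assumed to approximate the SAS procedure named in protocol 6.2), exponential hazards, fixed follow-up: N = 291.8, so 292, with power 80.0%. This matches the plan.
- Schoenfeld's formula gives 87 events. With a mean event proportion of (0.38 + 0.23)/2 = 0.305, N = 87/0.305 = 285.2, so 286, close to the plan.
- 292/0.78 = 374.4, against 374 in the plan.

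**3. What the scoring rule could do.** SAP 6.9 expects 22% to 33% of patients to have a second ablation, about 32 to 48 of 146 per arm. It does not say how many fall between week 6 and day 98, or in which rhythm. The shares below are therefore assumptions. No planning rates exist for AF/AT, so the primary's are used, taken as the rates under the SAP rule. The affected share is then rescored as failures, HR is recomputed as ln(S_T)/ln(S_A), and Lakatos power is taken at N = 292. The calculation keeps exponential hazards rather than placing the added events at 3 months, so it is approximate.

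| Share rescored, Tailored / Anatomical | Freedom, Tailored / Anatomical | HR | Power |
|---|---|---|---|
| 0 / 0 | 77% / 62% | 0.547 | 80% |
| 1% / 1% | 76% / 61% | 0.555 | 79% |
| 3% / 3% | 74% / 59% | 0.571 | 78% |
| 5% / 5% | 72% / 57% | 0.584 | 77% |
| 2% / 1% | 75% / 61% | 0.582 | 73% |
| 1% / 0 | 76% / 62% | 0.574 | 74% |
| 2% / 0 | 75% / 62% | 0.602 | 67% |
| 3% / 0 | 74% / 62% | 0.630 | 60% |
| 5% / 0 | 72% / 62% | 0.687 | 45% |

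In patients, 146 x 0.02 = 2.9 and 146 x 0.05 = 7.3 per arm.

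**4. False-positive side.** Suppose both arms are truly 62% under protocol 5.3.8 and the SAP rule lifts Tailored alone by 2%, 3% or 5%. The one-sided rejection rate is then about 5.5%, 7.7% or 14.5%, against a nominal 2.5%. A lift confined to Anatomical would push the rate below 2.5%.

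**The case against.** **Redos may not be blanked at all.** The parenthesis in SAP 6.2's first sentence exempts repeat procedures from blanking, so one could hold that every redo counts and that the next sentence only dates those in AF. This shows the section is unclear, but it does not supply a rule. The only sentence that scores such a redo is limited to spontaneous AF.

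**On the primary, the SAP is defensible.** This stands. Protocol 4.1 already ties redo failure to AF, and SAP 4.2 deliberately keeps non-AF redos inside the endpoint. The word spontaneous also has a good reason. Tailored redos follow the index approach (protocol 5.3.7), which includes inducing AF when it is absent (5.3.4), except for AT recurrences. The Anatomical redo rules mention no induction. Without the qualifier, induced AF could be counted as failure mainly in one arm.

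**SAP 4.2's reading of a single procedure might extend to AF/AT.** The SAP states it only for the primary. Extending it would keep AT redos inside an endpoint where AT is an event, which is the difficulty rather than an answer to it.

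**Few patients, unknown direction.** This also stands. Early redos are discouraged, and protocol 5.3.6 recommends months 3 to 9. A reader might infer that the rule favours Tailored, because protocol 5.3.4 warns of ablation patterns prone to AT. The documents do not support that: the passage is advice to reduce AT. At index, AT other than common flutter is mapped and ablated only in Tailored, so untreated AT could equally lead to early redos in Anatomical.

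**Conclusion.** The point holds for single-procedure AF/AT freedom and is a should-fix. SAP 6.2 departs from protocol 5.3.8 without declaring it and, followed as written, can score a twice-ablated patient with AT as free of AF/AT after one procedure.

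Three stronger readings are not supported:

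- **That the primary rule is wrong.** It is tied to AF by design. What remains is the redo for AF begun in sinus rhythm, which calls for a sensitivity analysis rather than a new definition.
- **That the bias favours Tailored.** No direction can be derived from the documents.
- **That the 22% to 33% redo rate bounds the number affected.** That rate covers all second ablations. Turning it into a count needs two shares that the documents do not give.

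Under the assumed shares, the effect is small if both arms are affected equally (power 77% to 79%). It becomes material only if it falls mainly on one arm, for example 67% power when 2% of Tailored and no Anatomical patients are affected. These figures borrow the primary's planning rates and serve only to show scale for the AF/AT endpoint.

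**What to change.** - **SAP 6.2:** limit the spontaneous-AF condition to AF-only endpoints. For single-procedure AF/AT freedom, restore protocol 5.3.8, so that any repeat ablation during blanking is an event at 3 months. Reword the parenthesis about repeat procedures to agree. The one-or-two-procedure endpoints allow a redo by definition and are not the subject of this point.
- **SAP section 7:** list the remaining departure from protocol 5.3.8, with its reason.
- **Primary endpoint:** keep the spontaneous-AF rule. Add one sensitivity analysis that counts every non-AT redo during blanking, including redos for AF begun in sinus rhythm, as an event at 3 months.
- **Leave alone:** do not rescore post-blanking redos by recorded indication. That rule is in neither document, would rest on an unblinded operator's label, and is not needed where Holter, TTM and ECG recordings already count.

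The cost is SAP wording and programming. SAP 4.2 and 6.2 presuppose that redo indication and presenting rhythm are known, but protocol Tables 7 and 9 do not list a redo indication, so confirm that the eCRF holds it. Reported freedom rates may be slightly lower.
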